**III. PURPOSE:**

Ketamine is an anesthetic agent, recently found to exert a rapid and potent antidepressant effect in severely depressed patients. Controversy exists in the field regarding how ketamine works in the brain and thus what underlies its rapid and profound antidepressant effects. A better understanding of the mechanism of the neuropsychiatric effects of ketamine are critically important, as pharmacological modulation of these effects can assist in the development of novel medications for the treatment of multiple psychiatric disorders including depression and schizophrenia.

The aim of the study is to provide insight into the impact of the immunosuppressant drug sirolimus (also known as rapamycin; known to have impact on depressive symptoms from molecular and preclinical studies), on the antidepressant effects of the prototypal rapid-acting antidepressant medication, ketamine. More specifically, the study will examine whether sirolimus shows significant interactive effects (i.e., synergy or antagonism) with ketamine in participants with treatment resistant depression as measured by the use of the clinician-administered Montgomery Asberg Depression Rating Scale (MADRS). We will also test the tolerability of the combined ketamine and sirolimus treatment. Secondary outcome measures are designed to measure the effects of sirolimus on the tolerability of ketamine.

- **Aim 1:** To characterize the effects of a single dose of sirolimus prior to a low dose of ketamine in subjects with antidepressant-resistant depressive symptoms.  
**Design:** 30 participants will be randomized into one of two groups at Time/Infusion 1 — ketamine+sirolimus (with placebo at Time 2) or ketamine+placebo (with sirolimus dose at Time 2).  
**Hypothesis:** Sirolimus will interact with ketamine by attenuating or potentiating the antidepressant effects.
- **Aim 2:** To examine the safety and tolerability of combined ketamine-sirolimus treatment.  
**Design:** The Systematic Assessment for Treatment Emergent Effects (SAFTEE) scale will be completed during each visit to compare the adverse events profile in the sirolimus and the placebo groups.

**Hypothesis:** Participants will tolerate the combined treatment with no residual adverse effects.

- **Aim 3:** To identify biological markers of the combined ketamine-sirolimus treatment.
- **Design:** Inflammatory biomarkers will be measured in 18 depressed participants who will receive open-label sirolimus+ketamine.

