Figure 1. The top figure illustrates the presence of synaptic (receives directly released glutamate) and extrasynaptic (receives glutamate "spillover" from the synapse) glutamate receptors. Ketamine may exert its treatment effects either indirectly by increasing glutamate release and stimulating the "go pathway" (synaptic AMPA glutamate receptors) or by blocking the "stop pathway" (extrasynaptic NR2B-containing NMDA glutamate receptors).

to produce anti-depressant effects in animals and to have beneficial effects in animal models of other neuropsychiatric disorders, perhaps by having anti-inflammatory effects in the brain. A study suggests that standard antidepressant administration reduces mTOR levels, an effect that would mimic the acute effects of sirolimus. Thus, if the direct effects of ketamine on the “stop pathway” pertain, then the antidepressant effects of sirolimus might *increase* the efficacy of ketamine.

[figure not shown]
Molecular studies in animals have found that synaptic deficits are precipitated by reduction in neurotrophins such as BDNF, and by inhibition of mTOR signaling pathway. Inhibition of mTOR signaling or reduction of BDNF leads to depressive-like behavior and blocks the effect of antidepressants in animal models of depression. Enhancing mTOR signaling or increasing BDNF produces antidepressant effects in preclinical studies. In humans, reduced central and peripheral BDNF levels were found in depressed patients and a functional variant of BDNF polymorphism (Val66Met) has been related to depression, especially in males. Together these data posit that enhancing BDNF and mTOR signaling leading to prefrontal synaptic formation (synaptogenesis), and reversal of stress/depression-induced neuronal atrophy and synaptic dysconnectivity is a required step for efficacious antidepressant treatment. Traditional antidepressants, targeting the monoaminergic system, were found to increase BDNF and synaptogenesis. However, these effects were only evident following chronic treatment, which is in line with the delayed antidepressant response to these drugs in humans. Therefore, it is proposed that rapid acting antidepressants would need to directly target the induction of mTOR signaling, the increase of BDNF levels, and the ultimate enhancement of prefrontal synaptogenesis.

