**Phase Three Research Procedures:**

We anticipate recruiting and screening approximately 35 male and female Veterans and non-Veterans/civilians, between the ages of 21-65 years, in order to meet our target sample of 18 subjects. Screening, enrollment and discontinuation criteria are identical to Phase 1 and 2. Treatment and study procedures are identical to Phase 2, except that participants will have only 1 treatment day (i.e., Infusion 1) with open-label sirolimus+ketamine (i.e., no Infusion 2 of placebo+ketamine). The weekly follow-up post Infusion 1, will be up to Day 29+ (i.e., 4 weeks follow-ups instead of 2 weeks). The follow-up period was extended considering the prolonged antidepressant effects of the combined sirolimus+ketamine treatment. The collection, processing and analysis of peripheral inflammatory biomarkers will be completed under a separate protocol and consent (i.e., CA0008). Participants in Phase 2, who consented to be contacted for future studies, will be invited to participate in Phase 3. This approach will both facilitate recruitment and reduce study risk as these participants who already received and well tolerated the study drug.

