***Ketamine Administration:***

Subjects will complete two test days separated by at least two weeks. Subjects will receive an infusion of ketamine (0.5 mg/kg infusion over approximately 40 minutes). All subjects will receive two ketamine infusions—once with a placebo and once with a single dose of sirolimus (6 mg, oral administration). The order of placebo and sirolimus is randomized. Note, the ketamine dose and route of administration are similar to that seen in previous investigations and has demonstrated high safety and tolerability.

A physician who is trained and has significant experience with both ketamine and infusion studies will oversee and administer the ketamine infusions. A nurse will accompany the subject throughout the study sessions, from the insertion of bilateral cannula for drug infusion and blood sampling, through to recovery following ketamine infusion.

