***Data Analysis:***

This study, investigating the impact of sirolimus on ketamine's rapid antidepressant effects, is the first of its kind. In order to assess study utility and to determine if medication dose adjustments may be useful, we plan to do interim analyses after completion of the first 6 subjects, with subjects randomized according to block randomization (block of six). We propose to study 30 patients, overall. This sample size is feasible within the funding available for this project and will provide 80% power for detecting ketamine-sirolimus interaction effects of moderate size ( $d'=.53$ ), assuming a two-tailed alpha=.05. The data analysis plan is provided only for the primary outcome variable, the MADRS score. The normality of the data will be tested initially using probability plots and the Kolmogorov-Smirnov tests. These data are frequently skewed and so we plan to analyze them using a non-parametric approach to repeated measures data. The data will be first ranked and then fitted with a mixed-effects model with an unstructured variance-covariance matrix and p values adjusted for ANOVA-type statistics. In these models sirolimus (active vs. placebo) and time will be fitted as within subjects variables. All interactions will be fitted. Age and sex will be treated as covariates/grouping factors. Post-hoc analyses will be conducted to interpret interactive effects significant at the p=0.05 level. Subject will be used as the clustering variable. Plasma ketamine and ketamine metabolite levels will be analyzed using linear mixed models. All secondary measures will be assessed using similar methodology. Behavioral measures of Phase 3 will use similar methodology. The collection, processing and analysis of peripheral inflammatory biomarkers will be completed under a separate protocol and consent (i.e., CA0008).

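### The 80% power is labelled as power for a ketamine-sirolimus interaction, but ketamine never varies, so it is power for the add-on effect of sirolimus, and synergy or antagonism cannot be estimated

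*Combined protocol and SAP*

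**What the plan says.** Section III (Purpose) says the study will examine "whether sirolimus shows significant interactive effects (i.e., synergy or antagonism) with ketamine", measured by MADRS. The Data Analysis section then says that 30 patients "will provide 80% power for detecting ketamine-sirolimus interaction effects of moderate size", with d'=.53 and a two-tailed alpha of .05. It describes the model as follows: "In these models sirolimus (active vs. placebo) and time will be fitted as within subjects variables". Ketamine is not listed as a factor.

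The treatments, by phase:

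- **Phase One** (Phase One Research Procedures): one sirolimus dose followed by ketamine, open label.
- **Phase Two** (Ketamine Administration): "All subjects will receive two ketamine infusions—once with a placebo and once with a single dose of sirolimus".
- **Phase Three** (Phase Three Research Procedures): "participants will have only 1 treatment day (i.e., Infusion 1) with open-label sirolimus+ketamine".

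The Background treats an effect of sirolimus on mood by itself as plausible. It cites antidepressant effects in animals, "perhaps by having anti-inflammatory effects in the brain", and says that if ketamine acts directly on the stop pathway, "then the antidepressant effects of sirolimus might" increase ketamine's efficacy. It also gives evidence in the other direction: "Inhibition of mTOR signaling or reduction of BDNF leads to depressive-like behavior and blocks the effect of antidepressants in animal models".

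The Significance section makes one branch of the conclusions conditional on synergistic effects. It and the Background both say that attenuation by sirolimus would establish mTOR stimulation as critical to ketamine's action.

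**The concern.** A claim of synergy or antagonism between two drugs concerns a departure from what each drug does separately. Estimating that departure needs both drugs to vary, and here only sirolimus does. The power statement is therefore attached to a quantity that the trial cannot estimate.

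This matters because mechanism is a main purpose of the study. If sirolimus has its own effect on mood, a better response with sirolimus may be simple addition, and a worse one may be sirolimus acting on mood independently of ketamine. Neither would show that the drugs interact. Phase 2 has reported augmentation, so the branch that the Significance section ties to synergy is the live one.

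**Working it through.** **1. Reproduce the 80%.** The inputs from Data Analysis are n = 30, d' = 0.53 and two-sided alpha 0.05. The Phase Two subjects section randomizes 45 to retain 30 completers, which fits 30 complete pairs.

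For a paired t-test on the within-patient difference, with d' on the SD of the paired differences:

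- noncentrality = 0.53 × √30 = 2.90, with 29 degrees of freedom
- power = **80.1%** (80.0% with the 28 degrees of freedom of a two-period crossover)
- effect detectable with 80% power = 0.529; smallest n for d = 0.53 is 30

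Other readings do not fit. A one-sided paired test gives 88.3%, and a parallel comparison of 15 versus 15 gives 28.9%. The stated figure is therefore that of a two-sided paired contrast.

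The plan does not say which SD d' refers to. If it is the raw SD, then dz = 0.53/√(2(1−ρ)), where ρ is an assumed within-person correlation:

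| ρ (assumed) | dz | power |
|---|---|---|
| 0.3 | 0.448 | 66% |
| 0.5 | 0.530 | 80% |
| 0.7 | 0.684 | 95% |

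The stated 80% thus matches d' on the SD of the differences, or on the raw SD with ρ = 0.5. Either way it is the same paired contrast.

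**2. What that contrast estimates.** Write mean improvement as KS (ketamine+sirolimus), KP (ketamine+placebo), S (sirolimus without ketamine) and N (neither).

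- Interaction = (KS − KP) − (S − N)
- Rearranged: KS − KP = (S − N) + interaction, that is, the effect of sirolimus by itself plus the interaction

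**3. Which of the four means are observed.**

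| Phase | KS | KP | S | N |
|---|---|---|---|---|
| One | yes | no | no | no |
| Two | yes | yes | no | no |
| Three | yes | no | no | no |

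S and N are absent throughout, so S − N is never estimated and the interaction is not identifiable. In Phase Two, sirolimus precedes ketamine by about two hours. That interval cannot supply a sirolimus-only course over the following days, and there is no untreated comparison.

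**4. The model.** With sirolimus and time as the within-subject factors, the available terms are sirolimus, time, and their interactions with each other and with age and sex. None is a ketamine-by-sirolimus term.

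**The case against.** The strongest defence is that the add-on question is already in the document. The title concerns the impact of sirolimus on ketamine's effects, and the Aim 1 hypothesis speaks of attenuating or potentiating them. On that view, interaction is loose usage. This stands in part: the Aim 1 wording is sound and the repair can borrow it. But the Purpose section gives the stricter definition explicitly, and the power statement names both drugs.

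Interaction could also mean sirolimus by time, a term that the model does contain and that the figure legend in the Significance section reports (p = 0.04). That term compares two trajectories, both under ketamine. An effect of sirolimus by itself that changes over time would also produce it.

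The protocol discloses a possible effect of sirolimus by itself and gives no human data on a single dose. Both are true. The disclosure makes the additive reading open, and the lack of data means its size is unknown.

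A reader might infer that the protocol misreports Phase 2 as synergy. It does not: the Background reports a prolonged effect and a tripled response rate, and the Significance wording is conditional. Nor does Phase 3 claim to test synergy; its stated aim is preliminary data on target engagement. The attenuation branch did not occur, so correcting it affects only the stated logic.

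**Conclusion.** The concern holds as a mislabelled effect and a limit on interpretation. The 80% is correct arithmetic (80.1%) for the add-on effect of sirolimus given ketamine. For synergy or antagonism the design has no estimate, and so no power figure. This follows from the treatments given and needs no numerical assumption; only the raw-SD reading of d' rests on an assumed correlation.

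Two consequences follow. The synergy condition in the Significance section cannot be established by any phase. Attenuation alone would not have shown that mTOR stimulation is critical, because a depressive effect of sirolimus by itself would look the same.

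A reader might also infer that the trial is underpowered or that its main finding is unsafe. The documents support neither. The power of the ranked repeated-measures test depends on an effect profile and correlations that the plan does not give. The add-on conclusion rests on a contrast that the design does estimate.

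**What to change.** - In the Purpose and Data Analysis sections, replace the interaction wording and its synergy-or-antagonism gloss with the effect on MADRS of adding sirolimus to ketamine (augmentation or attenuation, in line with the Aim 1 hypothesis). Attach the 80% to the paired sirolimus+ketamine versus placebo+ketamine contrast.
- Add one sentence saying that no phase can separate additive effects from synergistic or antagonistic ones.
- In the Background and Significance sections, change the synergy wording and the statements of certainty about mTOR to say that a result would be consistent with the mechanism.
- Optionally, state which SD d' refers to.

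Sample size, visits, treatment and analysis do not change. The cost is a narrower mechanistic claim.

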## V. SIGNIFICANCE:

The proposed project has potential to yield results critical to developing rapid-acting antidepressant medications based on the ketamine model. Specifically, if our results indicate

**Figure 1. The Study Drug Effect on Montgomery Åsberg Depression Rating Scale (MADRS).** (A) There is a significant main effect of time ( $F_{(8,245)} = 43.5, p < 0.0001$ ), demonstrating significant decrease in MADRS scores from baseline. There is also significant interaction between treatment and time ( $F_{(8,245)} = 2.0, p = 0.04$ ), with overall reduction in depression scores following treatment with rapamycin+ketamine (Rapamycin; blue line), compared to post placebo+ketamine (Placebo; red line). (B) Response rate was significantly higher following treatment with rapamycin+ketamine (Rapamycin; blue), compared to post placebo+ketamine (Placebo; red). NOTES: Response was defined as 50% improvement in MADRS from baseline; Error bars are standard errors of mean (SEM);  $d'$  = Cohen's  $d'$  effect size compared to pretreatment MADRS scores; Comparison at each time point is marked with \* for  $p \leq 0.05$  and t for  $p = 0.12$ ;

synergistic antidepressant effects, then we can pursue the combination of immunosuppressant and antidepressant therapy as a new approach to the treatment of depression. If we see antagonist effects of sirolimus on ketamine, then we will have learned that stimulating the mTOR signaling pathway is critical to the antidepressant effects of ketamine, resolving a major controversy in the field and implicating drugs facilitating mTOR signaling in the treatment of depression.

This proposal has potential to provide critical insights into the mechanisms of ketamine's antidepressant effects thus advancing our understanding of the neurobiology of depression and informing novel drug development for a new generation of rapid-acting antidepressants.

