**A. Phase Two Research Procedures (following DSMC approval) Subjects:**

We anticipate recruiting and screening approximately 75 male and female Veterans and non-Veterans/civilians, between the ages of 21-65 years, in order to meet our target enrollment goals. In order to account for subject dropouts and the potential need to discontinue subjects before study completion (see below for discontinuation criteria) and retain a sample of 30 subjects completing the double-blind treatment phase, 45 eligible subjects who meet criteria for Major Depressive Episode as determined by the Mini International Neuropsychiatric Interview (MINI) the study inclusion criteria outlines below, will be randomized into the study. Note, this study will not include a healthy control group as we are interested specifically in the antidepressant effects of ketamine and sirolimus and therefore require subjects with current depression.

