### **Research Plan and Study Procedures:**

This is a double blind, placebo-controlled, crossover, randomized controlled trial investigating the impact of sirolimus on ketamine's antidepressant effects in participants with antidepressant-resistant depressive symptoms. Participants will be treated twice with ketamine 0.5 mg/kg infused over 40 minutes, combined with a single dose of sirolimus 6 mg orally or placebo. The 2 infusions of ketamine are separated by at least 2 weeks interval because based on previous studies the majority of patients return to their baseline depression severity within this time period. A description of each study visit is provided here and summarized in Figure 3. See Table 1 for detail regarding the schedule of study events.

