#### ***Day 1 / Infusion 1:***

First, the MADRS assessment will be completed to confirm that the participant continues to have significant depressive symptoms (i.e. MADRS  $\geq 18$ ) prior to proceeding with Infusion 1. Participants will be rescheduled if depression severity was not met‡. If depression severity is confirmed, Infusion 1 procedures will be completed as follows:

- Subjects will present to the VACHS to complete vitals and provide a urine sample for drug and pregnancy testing.
- Subjects will receive a single 6 mg oral dose of sirolimus or placebo, dependent on their randomization. They will be monitored for any acute allergic reaction or other adverse event. Clinical assessments will be administered throughout the infusion visit, including PSWQ, PSQI, MADRS, QIDS-SR, SAFTEE, CGI, HAM-A, CADSS, PANSS\*\* (assessment measures are described below).
- Intravenous lines will be placed.
- A blood draw for sirolimus level will occur prior to the beginning of the ketamine infusion.
- Ketamine 0.5 mg/kg will be infused over approximately 40 minutes. Subjects will be monitored closely by study physician and nurse.
- A blood draw for ketamine will occur during the ketamine infusion.
- One additional blood draw for sirolimus will occur shortly before the participants are discharged from their study visit.
- Subjects may be discharged home after being cleared by a study physician.

‡ Screening procedures will be repeated if participant was not randomized within 60 days of screening. \*Blood pressure, heart rate, and oxygen saturation will be recorded every 10 minutes during infusion (T0-40 minutes). \*\* Items that could not change within a session, e.g. sleep and appetite, will be carried forward from the initial ratings.

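### The Phase 2 crossover model has no period term, so a difference between the two infusions goes into the error and, if sequences are unequal, into the sirolimus estimate

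*Combined protocol and SAP*

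**What the plan says.** The section Research Plan and Study Procedures states the design: "This is a double blind, placebo-controlled, crossover, randomized controlled trial". Each participant has two ketamine infusions, one with sirolimus and one with placebo, in randomised order and at least two weeks apart.

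The Data Analysis section ranks the MADRS scores and fits a mixed-effects model with an unstructured covariance: "In these models sirolimus (active vs. placebo) and time will be fitted as within subjects variables. All interactions will be fitted". Age and sex are covariates or grouping factors, and subject is the cluster. Neither period nor sequence is named there or elsewhere. The same approach extends beyond the primary outcome: "All secondary measures will be assessed using similar methodology".

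On numbers, the Phase Two Subjects paragraph allows for losses: to "retain a sample of 30 subjects completing the double-blind treatment phase, 45 eligible subjects" are to be randomised. Randomisation uses blocks of six.

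The results caption in Section V (Significance) reports a time effect with 8 numerator degrees of freedom and adds: "There is also significant interaction between treatment and time". It also shows tests at single times: "Comparison at each time point is marked with" a symbol for its p value.

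**The concern.** In a two-period crossover the treatment contrast is made across periods, so the usual model includes period. Time cannot stand in for it here. Aim 1 and the Day 0 text do use the word time for the two infusions, but 8 numerator degrees of freedom mean nine levels, which are assessment times within an infusion. A two-level period factor would have 1. Fitting all interactions only crosses factors already listed.

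A period difference is plausible. Infusion 2 is a second ketamine exposure, and the entry rules differ. Infusion 1 needs a MADRS of at least 18 ("Participants will be rescheduled if depression severity was not met"); Infusion 2 needs a score within 20% of baseline. A participant with baseline 30 can start Infusion 2 at 0.8 × 30 = 24. One with baseline 18 to 21 can start at 15 to 17 (0.8 × 18 = 14.4; 0.8 × 21 = 16.8), below the Infusion 1 threshold.

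At stake are the precision of the sirolimus contrast, its size if completers are unequal by sequence, and the single-time comparisons. The Background section uses the Phase 2 result to justify Phase 3.

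**Working it through.** **1. The plan's own figure.** Inputs from Data Analysis: 30 patients, d' = 0.53, two-sided alpha 0.05. A paired t-test has noncentrality 0.53 × √30 = 2.90 on 29 df, giving power 80.1%. A two-sample test at 15/15 would give 29%. The stated 80% is therefore a paired calculation with no period term.

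**2. Algebra.** Let τ be the sirolimus effect and π the period difference (Infusion 2 minus Infusion 1), both in SDs of the paired difference. The expected sirolimus-minus-placebo difference is τ − π in the n₁ people given sirolimus first and τ + π in the n₂ given placebo first. With N = n₁ + n₂:

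- Without period, the mean difference estimates τ + π(n₂ − n₁)/N, and the variance grows by π²[1 − ((n₂ − n₁)/N)²].
- With period, the estimate is the average of the two sequence means. It is unbiased whatever π is, with SE ½√(1/n₁ + 1/n₂) on N − 2 df.

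**3. Bias.** The share of π entering the estimate is 2/30 = 6.7% at 14/16 and 4/30 = 13.3% at 13/17. With π = 0.22 (an assumption; 0.22 × 9 = 2 points if the SD is 9), bias is 0.22 × 2/30 = 0.0147, or 2.8% of 0.53, at 14/16. At 13/17 it is 0.22 × 4/30 = 0.0293, or 5.5%. The sign follows that of π.

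**4. Power of the paired contrast** (noncentral t with period; simulation without it where π is not 0; where two values are given, they are for the two signs of π):

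| Completers | With period | Without, π = 0 | Without, π = ±0.11 | Without, π = ±0.22 |
|---|---|---|---|---|
| 15/15 | 80.0% | 80.1% | 80% | 79% |
| 14/16 | 79.8% | 80.1% | 79% or 81% | 76% or 81% |
| 13/17 | 79.3% | 80.1% | 78% or 82% | 74% or 83% |

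At π = ±0.5, larger than anything the documents suggest, power without the term is 73% at 15/15 and 60% or 83% at 13/17, where bias is 12.6%. Type I error without the term is 4.5% to 4.8% at 0.22. It rises above nominal only at splits more extreme than these; for example, it is 10% at 10/20 with π = 0.5.

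**5. How likely unequal completers are.** Forty-five people are seven full blocks (21/21, taking 1:1 allocation) plus three from an eighth. If the 30 completers are a chance subset (hypergeometric, averaged over the last three assignments), exactly 15/15 has probability 24% and 14/16 or more unequal 76%. The probability of 13/17 or more unequal is 36% (35% to 43% by how the 45 divide), and of 10/20 or more unequal 0.5%.

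**6. The treatment-by-time test.** This was checked with a simplified rank-based ANOVA-type test on 30 complete pairs and nine times, without age or sex. The MADRS profile, SDs (6 before and 9 after infusion) and correlations (0.5 between infusions, 0.6 per time step) are assumed, and the benefit was set to give about 80% power. Absolute levels are illustrative; the contrast with and without period is the result. The assumed shift is 2 points.

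- Constant shift: treatment-by-time power is 79% to 80% with or without the terms. The last-time comparison becomes 81% or 85% (14/16) and 77% or 86% (13/17), against 81% to 84% with period.
- Shift at the last three times only: treatment-by-time power is 78% to 80% (15/15), 76% or 81% (14/16) and 73% or 83% (13/17), against 78% to 80% with period and period-by-time.
- Type I error of the treatment-by-time test is at or below 5.1% (simulation error about 0.3 points).

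**7. Can the terms be fitted?** For 30 people, two infusions and nine times, sirolimus, time and their interaction use 18 columns. Period and period-by-time bring this to 27 (rank 27), and sequence to 28 (rank 28). Adding sirolimus-by-period gives 29 columns but rank 28: it is the same contrast as sequence.

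**The case against.** The strongest reply is that the effect is small and its cause assumed. At 0.22 SD, averaged over the chance splits, mean absolute bias is about 3.6% of the sirolimus effect and power about 78.5%. The plan is powered for the interaction, and a constant shift cancels from that test; harm there needs a period-by-time difference, for which the documents give neither size nor shape. The 20% rule can also be read as admitting scores above baseline (36 for baseline 30). Order is randomised in blocks, and with equal sequences the estimate is unbiased and the test slightly conservative. A mixed model need not be confined to complete pairs, so the 2/30 and 4/30 shares may not carry over exactly. Finally, Phase 2 has been analysed, and the caption does not list model terms, so period may have been fitted.

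Most of this stands as a limit on size. The figures are conditional on an assumed period effect and on complete pairs, and the omission is certain only for the written plan. None of it supplies the missing term. Balance at randomisation does not secure balance among completers, and balance removes bias without restoring the lost precision. The single-time comparisons do not benefit from the cancellation.

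**Conclusion.** The concern holds. The written model for a two-period crossover omits period and period-by-time, and no other section supplies them. The likely consequence is modest. With a period effect of 0.22 SD, 30 complete pairs and d = 0.53, power is 79% at 15/15 and between 74% and 83% at 13/17, with bias of at most 5.5% of the sirolimus effect at these splits. That 0.22 SD is an assumption, not a ceiling. Simulating the entry rule under assumed MADRS values put the score before Infusion 2 at 1.8 to 3.2 points below that before Infusion 1, but this concerns the pre-infusion score only.

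This does not show that the reported interaction (p = 0.04) is a false positive, since type I error is not inflated at the splits considered. A refit could still move the estimate, its p value and the single-time comparisons in either direction. It should be fixed, because the remedy is standard and nearly free.

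**What to change.** - Name period (Infusion 1 or 2) and period-by-time as fixed effects in the primary model and in the secondary analyses that follow it. State that time means assessment time within an infusion.
- Limit the instruction to fit all interactions so that sirolimus-by-period is not fitted together with sequence. Sequence may be included as a between-subject term in its place.
- Refit the Phase 2 data and restate the result, including the single-time comparisons, or state that these terms were already in the fitted model.
- Report completers by sequence, so that readers can judge the possible bias directly.

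The cost is one refit on data already collected and 1 + 8 = 9 more fixed-effect parameters. If there is no period effect, the paired contrast loses 80.1 − 80.0 = 0.1 points of power at 15/15, 80.1 − 79.8 = 0.3 at 14/16 and 80.1 − 79.3 = 0.8 at 13/17. Carryover, and Infusion 2 data missing because of the entry rule, are separate issues that this change does not resolve.
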